Protocol

Title: Producing a Fully Asynchronous Online Savvy Program

NCT Number: NCT04951037

Protocol Date: May 14, 2020

PROTOCOL TITLE: Producing a Fully Asynchronous Online Savvy Program

PRINCIPAL INVESTIGATOR:

Name: [name], RN

Department: Nursing

[contact]

Email Address: [contact]

Name: [name] DNP, GNP-BC, AGPCNP-BC, FAANP

Department: Nursing

[contact]

Email Address: [contact]

VERSION: Version 3- 5-14-2020

FUNDING SOURCE: Pending funding from the National Institute on Aging (NIA)

REVISION HISTORY

Revision #	Version Date	Summary of Changes
3	5-14-2020	Updated and provided different options to obtaining consents

Table of Contents

1. Study Summary	4
2. Objectives.....	4
3. Background	4
4. Study Endpoints	4
5. Study Intervention / Design	4
6. Procedures Involved.....	5
7. Data and Specimen Banking.....	5
8. Sharing of Results with Participants.....	5
9. Study Timelines	6
10. Subject Population.....	6
11. Vulnerable Populations	6
12. Local Number of Participants	6
13. Recruitment Methods.....	7
14. Withdrawal of Participants	7
15. Risks to Participants.....	7
16. Potential Benefits to Participants	7
17. Data Analysis, Management and Confidentiality.....	8
18. Provisions to Monitor the Data to Ensure the Safety of Participants.....	8
19. Provisions to Protect the Privacy Interests of Participants and Confidentiality of Participants' identifiable data.....	9
20. Economic Burden to Participants	9
21. Consent Process.....	9
22. Setting.....	12
23. Resources Available	12
24. Multi-Site Research when Emory is the Lead Site	12
25. References	13

1. Study Summary

Study Title	Producing a Fully Asynchronous Online Savvy Program
Study Design	Pilot/Feasibility Study
Primary Objective	We are seeking to develop and test a fully online, self-administered psychoeducation program to enhance the caregiving mastery of family and friends who provide unpaid care for persons living with Alzheimer's and similar dementia disorders (PLWD).
Secondary Objective(s)	n/a
Research Intervention(s)/Interactions	Fully asynchronous online caregiver education program
Study Population	Dementia caregivers
Sample Size	Aim 1 = 20; Aim 2 = 60
Study Duration for individual participants	Aim 1 participants-5 months Aim 2 participants-3 months
Study Specific Abbreviations/ Definitions	ADRD = Alzheimer's Disease and Related Dementias PLWD = person living with Alzheimer's and similar dementia disorders.

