Funding Source (if any)	Pending funding from National Institute on Aging

2. Objectives

To make a program that appears to enhance caregiving mastery even more accessible and available to a growing number of dementia family caregivers, we seek to pursue two aims:

Aim 1. Develop a fully asynchronous online Savvy program that incorporates learning activities that promote both knowledge and skill acquisition and develop/enhance caregivers' felt-sense of caregiving mastery.

With input from clinicians, educators, Tele-Savvy facilitators, and caregiver advisors, and assisted by the Roybal Center's Design Studio, we will iteratively develop a storyboard and scripted curriculum for this online educational program. Then, in collaboration with our educational design consultant, we will modify/produce the text and video assets and place them on a continuing education platform that promotes active learning.

Aim 2. Establish the feasibility, acceptability and preliminary efficacy of the online program.

We will use a number of highly reliable channels to recruit 60 family caregivers to take part in a no-control trial of the program, gathering data – at baseline, immediately upon course completion and at 3 months post-baseline – on caregiver distress measures (depression, strain, burden, anxiety), caregiver competence/ mastery, and care recipient quality of life. We will administer investigator-developed evaluation surveys to assess feasibility and acceptability and ad lib improvement comments. We will also seek formative evaluation input through at least 15 semi-structured debriefing interviews, post completion.

3. Background

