Three key preliminary findings from the online Tele-Savvy program drive and support this pilot project. The first finding is that Tele-Savvy seems to have worked. It appears to have demonstrated efficacy in reducing the distress associated with dementia family caregiving and to have increased caregivers' sense of mastery in carrying out the caregiving role. Preliminary results from the first 220 participants in the baseline to six month segment of this three arm trial (Tele-Savvy; Healthy Living attention control; and Usual Care) indicate that Tele-Savvy participants demonstrated statistically significant group-by-time reductions in depression and caregiver strain and statistically significant group-by-time increases in caregiver mastery, compared to those in the other two groups. The second finding is that participants were highly adherent to the asynchronous portion of Tele-Savvy (36 8-15 minute daily video lessons that are viewed whenever and as often as participants wish); they spent, on average, more than 8 hours watching the videos over the 43-day course of the program. The third finding is that the group nature of the synchronous portion of the program constitutes a barrier for participation and a threat to scalability. A substantial number of individuals who consented to be a part of the trial of the program were never able to participate because their schedules precluded incorporating them into online groups.

4. Study Endpoints

Primary endpoints that will be measured are depression (CES-D), burden (Zarit), anxiety (STAI), mastery (Pearlin), and care recipient behavior (RMBPC).

5. Study Intervention / Design

The proposed intervention for this study is a Fully Asynchronous Online Savvy program. This proposed research follows the NIH Stage model for intervention development. In Aim

1, we will be engaging in Stage 1A of the model. In Aim 2, we will be engaging in the Stage 1B of the NIH Stage Model.

6. Procedures Involved

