All Aim 2 research materials will be gathered by a trained interviewer through distance means (by phone or videoconference). The data will be in the form of an interview consisting, principally, of well-established instruments focused on the participant's experience of caregiving and his/her observations about and reactions to the care recipient's behavior and well-being. Interviews will be collected at baseline, 2 months, and 3 months. The data for the study will be entered into a secured database using an electronic data capture program such Research Electronic Data Capture (REDCap). The database will be stored on a secure password-protected server and not on individual desktop computers. The code sheet will be password protected and the password will be updated annually. A semi-structured interview will be conducted with a subsample of Aim 2 participants. These interviews will focus on caregivers' experiences of providing care during the pandemic and on their experience of the course developed by this project.

7. Data and Specimen Banking

The proposed Aim 2 research will include data from a community-based sample of 60 informal caregivers of persons living with Alzheimer's disease or a similar neurocognitive illness. In addition to base demographics, the dataset will include four common measures of caregiver depression, anxiety, burden, and mastery. The final dataset also will include additional self-report

measures based on current literature on caregivers. The final dataset will be stored in the Roybal Center data repository. Data from this pilot study will be available to qualified researchers through a data sharing agreement that is fully consistent with NIH data sharing policies and applicable laws and regulations as well as official policies and practices established by the Roybal Center at Emory. Although these data will be de-identified prior to release for sharing, there remains a possibility of deductive disclosure of participants with unusual characteristics. Therefore, this data sharing agreement will require: 1) a commitment only to use the data for research purposes and not to identify any individual participant; 2) a commitment to securing the data using appropriate computer technology; and 3) a commitment to destroy or return the data after analyses are completed.

8. Sharing of Results with Participants

Study results will not be shared with participants or others (e.g., the subject's primary care physicians).

9. Study Timelines

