We will recruit approximately 20 individuals (e.g., clinicians, educators, Tele-Savvy facilitators, and caregiver advisors) for Aim 1 activities from the investigative team's professional network. The proposed sample size of 20 for Phase 1 is justified by the proposed qualitative approach. For Aim 2, we will recruit the 60 subjects by reaching out to caregivers through a number of channels: [name] IMCC has a current PWD enrollment of 625, most of whom are community dwelling; [name] work with Atlanta area churches and African American families affected by dementia provides a large recruitment base; [name] connections with Emory's Alzheimer's Disease Research Center (ADRC) and the statewide diagnostic and care planning Georgia Memory Net also offers a large base. In addition, [name] maintains contact with numerous organizations across the country that offer the Savvy Caregiver in-person program, and he will seek their assistance in recruitment. Existing collaborations with other ADRCs and organizations offering Savvy provides an even larger recruitment base. We will also recruit through various social media platforms. Recruitment material will provide information about the trial and phone and email contacts to indicate further interest. The proposed sample size of 60 subjects is modest, reasonable, and justified by through Browne's general rule of using a minimum of 30 participants to have the capacity to estimate a parameter for feasibility.

Verbal and email scripts (see attached) will be used by the investigative team to recruit through their professional networks for Aim1.

Flyers (see attached) will be used to recruit across all proposed platforms. For recruiting on social media, potential participants will see the flyer and will be directed to contact MPI for further information.

Potential participants will be screened via phone according to inclusion criteria. If eligibility criteria are met, participant will be consented by a member of the research team.

Participants will receive a \$20 honorarium (gift card) for their completion of focus groups or timepoint interviews. Payments will be administered via mail to participants after their participation in each focus group and timepoint interview.

14. Withdrawal of Participants

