We anticipate participants will be withdrawn from the study without consent when they do not respond to scheduling baseline and at least 1 follow up interview. When participants self-select to withdraw from the study, one of the PIs will follow up with the participant and confirm withdrawal. Participants can withdraw from the study at any time with no consequence. The team will then discuss if partial data can be included in analysis.

15. Risks to Participants

Protection against risks from participation in Design Studio activities. Participants in the sessions will be identified only by first names, and transcripts of the audio-recorded Design Studio sessions will be fully anonymized, so the threat to confidentiality will be virtually eliminated.

Risks from Research Interviews. There is virtual no risk to the confidentiality of the research data. All study subjects will be assigned ID numbers. The file linking the ID numbers to subjects' identities will be kept in a separate locked filing cabinet in MPI [name]' locked office. There is a minimal risk that participants might find that some elements of the research questionnaires provoke transient emotional responses. The research interviewer will be trained to be alert for such moments and will be able to provide reassurance, offer a break from the interview, and/or reschedule the remaining portion of the interview. In addition, a protocol from another study will be in place to identify participants whose scores on a set of three questionnaires exceed established limits; in such cases, one of the MPIs will contact the individual to check on his/her safety and well-being.

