preliminary analyses, descriptive statistics and frequency distributions will be examined to identify outliers and ensure integrity of merged files. Analysis of variance (ANOVA) with repeated measures, non-parametric Kruskal-Wallis ANOVA, and Chi-Square tests will be used to assess preliminary efficacy and establish effect size for a larger study. Internal consistency will be examined using Cronbach's alpha and associated statistics (e.g., item-total correlations, alpha if item deleted). Formal test-retest/inter-rater reliability coefficients will be computed as data are concatenated. NVivo will be used to analyze qualitative data such as focus groups for Aim 1 and interviews for Aim 2. All audio recordings will be transcribed verbatim. The databases will be stored on a secure password-protected server and not on individual desktop computers. The code sheet will be password protected and the password will be updated annually.

The study team for this study will be comprised of the Principal Investigators (Drs. [name] and [name]), and Co-Investigator ([name]). The MPIs will be responsible for the day to day operations of the study including recruitment and data collection management and analysis. The administrative site will be at Emory University, Nell Hodgson Woodruff School of Nursing. All team members have completed CITI training. Study-specific training for staff who will be obtaining data by interview.

[name] is the primary individual charged with identification and reporting of all adverse events (AE) and serious adverse events (SAE). [name] will provide systematic routine monitoring for the following central elements: protocol eligibility (direct source documentation of eligibility as defined in the protocol), appropriateness of consent documentation, and timeliness and accuracy of data. Monitoring reports will be conducted on a bi-weekly basis and as needed, and will be reviewed at the weekly core team meeting of the investigator team.

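### Section 17 names Kruskal-Wallis for efficacy but not what it compares; used across visits in this one-group trial, it would ignore the pairing and could miss small changes

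*Combined protocol and SAP*

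**What the plan says.** Section 17 gives the whole efficacy analysis in one sentence: "Analysis of variance (ANOVA) with repeated measures, non-parametric Kruskal-Wallis ANOVA, and Chi-Square tests will be used to assess preliminary efficacy". The same sentence adds a second purpose, to obtain an effect size for a later, larger study. It gives no outcome, factor or grouping variable for any of the three tests, and no significance level. No paired rank test is named anywhere.

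The design is set out elsewhere:

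- Section 2 (Aim 2): the team will "recruit 60 family caregivers to take part in a no-control trial of the program".
- Section 6: "Interviews will be collected at baseline, 2 months, and 3 months". The same caregivers are seen each time.
- Section 4: five primary endpoints, all scale scores (CES-D, Zarit, STAI, Pearlin mastery, RMBPC).
- Section 1: the design is a "Pilot/Feasibility Study".
- Section 13, repeated in Section 23: the sample size rests on a rule of "using a minimum of 30 participants to have the capacity to estimate a parameter for feasibility", not on power.

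**The concern.** Kruskal-Wallis compares independent groups. Aim 2 has one group, and the plan defines no subgroup, exposure level or other between-person comparison for efficacy. The only efficacy contrast it does define is time within caregiver. Read against that design, the test either has no defined comparison or would be run on three sets of scores from the same people as if they came from different people.

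In the second case the test's reference distribution includes between-person variation that cancels when each caregiver is compared with herself or himself. With positive correlation between visits, the test then rejects too rarely. The risk is a report of no change on a scale that did change, and disagreement with the ANOVA that the rank test is presumably there to support. A rank test is most useful when scores are skewed, so the choice of rank test matters for these scales.

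**Working it through.** **Inputs from the plan.** n = 60, one group, three visits, five scale endpoints. There is no power figure to reproduce. Only the recruitment arithmetic in Section 23 can be checked: 5 months × 12 per month = 60, which agrees.

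**Inputs assumed, because the plan gives none.** Test level 5%; equal within-person correlation r = 0.3, 0.5 or 0.7 between visits; the same shift of d SD at both follow-ups; complete data. All triplets below are in the order r = 0.3/0.5/0.7.

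**Step 1: type I error by hand.** With three visits the Kruskal-Wallis statistic is referred to chi-square on 2 df, critical value 5.991. If the ranks correlate at about r within person, differences between visit mean ranks have only (1 − r) of the variance the test assumes. So

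true alpha ≈ P(chi-square on 2 df > 5.991/(1 − r)) = exp(−2.996/(1 − r)).

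- r = 0.3: exp(−4.28) = 1.4%
- r = 0.5: exp(−5.99) = 0.25%
- r = 0.7: exp(−9.99) = 0.005%

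Simulation with normal scores (10,000 trials per cell) gives 1.44/0.37/0.03%. The last figure is 3 rejections in 10,000. The hand formula runs a little low because rank correlation is slightly below score correlation. Friedman and repeated-measures ANOVA stay near 5%.

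**Step 2: what pairing is worth.** For repeated-measures ANOVA with means (0, d, d), the non-centrality is n × (2d²/3)/(1 − r). At d = 0.3 this is 60 × 0.06/(1 − r) = 3.6/(1 − r) = 5.1/7.2/12.0. Information grows as r rises. Kruskal-Wallis across visits does not use it.

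**Step 3: power by simulation, n = 60.**

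| Scores, change | Kruskal-Wallis | Friedman | Repeated-measures ANOVA | Either of two Wilcoxon contrasts at 0.025 |
|---|---|---|---|---|
| Normal, 0.3 SD | 30/26/18% | 38/51/74% | 50/67/88% | 51/67/87% |
| Normal, 0.5 SD | 81/84/87% | 82/93/99.5% | 93/98/100% | 92/98/99.9% |
| Skewed, 0.3 SD | 50/48/45% | 58/74/94% | 48/63/84% | 59/74/92% |
| Skewed, 0.5 SD | 96/97/99% | not run | not run | 95/99/100% |

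The skewed rows use 5,000 trials per cell, integer scores with skewness about 1.4, limited to 0–60. At 0.3 SD with normal scores, Kruskal-Wallis and the ANOVA reach different conclusions in 21/41/69% of trials.

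**Step 4: does one paired rank test always win?** No. With skewed scores and a 0.3 SD change at one follow-up only (1,500 trials per cell), the Wilcoxon pair has 41/53/80%, Friedman 56/73/91% and Kruskal-Wallis 50/46/43%. At r = 0.3 the Wilcoxon pair is then weaker than Kruskal-Wallis. With normal scores and equal change at both follow-ups, the order of the two paired tests reverses: Wilcoxon 51/67/87%, Friedman 38/51/74%.

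**The case against.** The strongest reply is that the plan never says Kruskal-Wallis will be run across visits. What the text shows is under-specification. The team might compare change scores between caregiver groups, where the test is valid. That stands: use across visits is reached by elimination, and the power figures apply only if that use is made. It does not remove the point, because no such groups are defined and either reading needs the same clarification.

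Second, the same sentence names repeated-measures ANOVA, which respects the pairing. That also stands. A reader might infer that the efficacy analysis as a whole is invalid, or that it would produce false positives. The documents support neither: the ANOVA fits the five scale endpoints, and the error from Kruskal-Wallis runs in the conservative direction.

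Third, the size is assumed throughout and shrinks in places. At 0.5 SD with skewed scores the loss is practically gone. At 0.3 SD with skewed scores and r = 0.3, Kruskal-Wallis is level with the ANOVA (50% against 48%). At r = 0.5 its shortfall against the ANOVA is 15 points with skewed scores, against 41 with normal scores. These limits are accepted.

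A reader might also extend the criticism to chi-square. It would share the fault only for a categorical outcome followed over time, and the plan defines none, so no loss is claimed there.

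**Conclusion.** The point holds in conditional form, as a minor correction. Section 17 does not say what its only rank test compares, and that test does not fit the only efficacy contrast the design offers. If it is used across visits, small changes could be missed: for 0.3 SD with normal scores, power is 8/26/55 points below Friedman and 21/41/69 points below the ANOVA (differences of the unrounded simulation figures). At 0.5 SD with normal scores the shortfall against Friedman is about 0/9/12 points.

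These sizes rest on the assumed level, correlations, distributions and change pattern. The weight is further limited because this is a pilot whose sample size is not based on power, and because the valid repeated-measures ANOVA is already named.

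**What to change.** In Section 17:

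- For change over time, replace Kruskal-Wallis with a paired rank test: Friedman across the three visits, with Wilcoxon signed-rank for baseline against each follow-up as the pairwise contrasts.
- Keep Kruskal-Wallis and chi-square only for comparing distinct people, and name that comparison.
- State that the repeated-measures analysis leads.
- Report mean within-person change with a 95% confidence interval as the effect size for the later study. The plan does not currently name an interval.

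The cost is a few sentences, with no extra data, visits or participants.

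There are downsides. Friedman, like the standard repeated-measures ANOVA, drops anyone with a missing visit. Wilcoxon contrasts keep more people but need a stated alpha split if they serve as the main rank test, and they can have less power than Friedman when change occurs at only one follow-up. Neither paired test is better under every pattern.

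As an illustration, assume 10% miss only month 2 and another 10% miss only month 3. Then 60 − 6 − 6 = 48 caregivers are complete and 60 − 6 = 54 pairs remain for each contrast. At 0.3 SD with normal scores and equal change at both follow-ups, power is 41/55/78% for the ANOVA, 32/43/64% for Friedman and 47/63/84% for either Wilcoxon contrast.

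Section 14 does not settle who is kept. It provides for withdrawal of participants "when they do not respond to scheduling baseline and at least 1 follow up interview", which can be read as keeping those with baseline and one follow-up. For those who choose to withdraw it says "The team will then discuss if partial data can be included in analysis". The change proposed here does not resolve that, nor multiplicity across the five endpoints.
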